12.2 Appendix: Response Assessment of Hodgkin and Non-Hodgkin Lymphoma (Lugano Classification)

Response Assessment of Hodgkin and Non-Hodgkin Lymphoma (Lugano Classification)

Response / Site	PET-CT-Based Response	CT-Based Response
Complete	Complete metabolic response	Complete radiologic response (all of the following)
Lymph nodes and extralymphatic sites	
 Score 1, 2, or 3* with or without a residual mass on 5PS** 
Note: Uptake may be greater than normal mediastinum and/or liver in Waldeyer's ring or extranodal sites with high physiologic uptake or with activation within spleen or marrow (e.g., with chemotherapy or myeloid colony-stimulating factors). In this circumstance, complete metabolic response may be inferred if uptake at sites of initial involvement is no greater than surrounding normal tissue even if the tissue has high physiologic uptake
	
 Target nodes/nodal masses must regress to ≤ 1.5 cm in LD No extralymphatic sites of disease
Nonmeasured lesion	
 Not applicable 	
 Absent
Organ enlargement	
 Not applicable 	
 Regress to normal
New lesions	
 None 	
 None
Bone marrow	
 No evidence of FDG-avid disease in marrow 	
 Normal by morphology; if indeterminate, IHC negative
Partial	Partial metabolic response	Partial remission (all of the following)
Lymph nodes and extralymphatic sites	
 Score 4 or 5** with reduced uptake compared with baseline and residual mass(es) of any size. At interim, these findings suggest responding disease. At end of treatment, these findings indicate residual disease. 	
 $\geq 50\%$ decrease in SPD of up to 6 target measurable nodes and extranodal sites When a lesion is too small to measure on CT, assign 5 mm \times 5mm as the default value. When no longer visible, 0 \times 0 mm For a node >5 mm \times 5 mm, but smaller than normal, use actual measurement for calculation
Nonmeasured lesion	
 Not applicable 	
 Absent/normal, regressed, but no increase
Organ enlargement	
 Not applicable 	
 Spleen must have regressed by $>50\%$ in length beyond normal
New lesions	
 None 	
 None

Response Assessment of Hodgkin and Non-Hodgkin Lymphoma (Lugano Classification)

Response / Site	PET-CT-Based Response	CT-Based Response
Bone marrow	
 Residual uptake higher than uptake in normal marrow but reduced compared with baseline (diffuse uptake compatible with reactive changes from chemotherapy allowed). If there are persistent focal changes in the marrow in the context of a nodal response, consideration should be given to further evaluation with MRI or biopsy or an interval scan 	
 Not applicable
No response or stable disease	No metabolic response	Stable disease
Target nodes/nodal masses, extranodal lesions	
 Score 4 or 5 with no significant change in FDG uptake from baseline at interim or end of treatment 	
 <50% decrease from baseline in SPD of up to 6 dominant, measurable nodes and extranodal sites; no criteria for progressive disease are met
Nonmeasured lesions	
 Not applicable 	
 No increase consistent with progression
Organ enlargement	
 Not applicable 	
 No increase consistent with progression
New lesions	
 None 	
 None
Bone marrow	
 No change from baseline 	
 Not applicable
Progressive disease	Progressive metabolic disease	Progressive disease (requires at least 1 of the following)
Individual target nodes/nodal masses	
 Score 4 or 5 with an increase in intensity of uptake from baseline and/or 	
 PPD progression
Extranodal lesions	
 New FDG-avid foci consistent with lymphoma at interim or end of treatment assessment 	
An individual node/lesion must be abnormal with:
 
 LDi > 1.5 cm and Increase by $\geq 50\%$ from PPD nadir and An increase in LDi or SDi from nadir 0.5 cm for lesions ≤ 2 cm 1.0 cm for lesions > 2 cm In the setting of splenomegaly, the splenic length must increase by > 50% of the extent of its prior increase beyond baseline (e.g., a 15-cm spleen must increase to > 16 cm). If no prior splenomegaly, must increase by at least 2 cm from baseline New or recurrent splenomegaly
Nonmeasured lesions	
 None 	
 New or clear progression of preexisting nonmeasured lesions

Response Assessment of Hodgkin and Non-Hodgkin Lymphoma (Lugano Classification)

Response / Site	PET-CT-Based Response	CT-Based Response
New lesions	
 • New FDG-avid foci consistent with lymphoma rather than another etiology (e.g., infection, inflammation). If uncertain regarding etiology of new lesions, biopsy or interval scan may be considered 	
 • Regrowth of previously resolved lesions • A new node > 1.5 cm in any axis • A new extranodal site > 1.0 cm in any axis; if < 1.0 cm in any axis, its presence must be unequivocal and must be attributable to lymphoma • Assessable disease of any size unequivocally attributable to lymphoma
Bone marrow	
 • New or recurrent FDG-avid foci 	
 • New or recurrent involvement

Abbreviations: 5PS, 5-point scale; CT, computed tomography; FDG, fluorodeoxyglucose; IHC, immunohistochemistry; LD_i, longest transverse diameter of a lesion; MRI, magnetic resonance imaging; PET, positron emission tomography; PPD, cross product of the LD_i and perpendicular diameter; SD_i, shortest axis perpendicular to the LD_i; SPD, sum of the product of the perpendicular diameters for multiple lesions.

* A score of 3 in many patients indicates a good prognosis with standard treatment, especially if at the time of an interim scan. However, in trials involving PET where de-escalation is investigated, it may be preferable to consider a score of 3 as inadequate response (to avoid undertreatment). Measured dominant lesions: Up to six of the largest dominant nodes, nodal masses, and extranodal lesions selected to be clearly measurable in two diameters. Nodes should preferably be from disparate regions of the body and should include, where applicable, mediastinal and retroperitoneal areas. Non-nodal lesions include those in solid organs (e.g., liver, spleen, kidneys, lungs), GI involvement, cutaneous lesions, or those noted on palpation. Nonmeasured lesions: Any disease not selected as measured, dominant disease and truly assessable disease should be considered not measured. These sites include any nodes, nodal masses, and extranodal sites not selected as dominant or measurable or that do not meet the requirements for measurability but are still considered abnormal, as well as truly assessable disease, which is any site of suspected disease that would be difficult to follow quantitatively with measurement, including pleural effusions, ascites, bone lesions, leptomeningeal disease, abdominal masses, and other lesions that cannot be confirmed and followed by imaging. In Waldeyer's ring or in extranodal sites (e.g., GI tract, liver, bone marrow), FDG uptake may be greater than in the mediastinum with complete metabolic response, but should be no higher than surrounding normal physiologic uptake (e.g., with marrow activation as a result of chemotherapy or myeloid growth factors).

** PET 5PS: 1, no uptake above background; 2, uptake ≤ mediastinum; 3, uptake > mediastinum but ≤ liver; 4, uptake moderately > liver; 5, uptake markedly higher than liver and/or new lesions; X, new areas of uptake unlikely to be related to lymphoma.

Reference: Cheson BD, Fisher RI, Barrington SF, Cavalli F, Schwartz H, Lister TA. Recommendations for initial evaluation, staging, and response assessment of Hodgkin and Non-Hodgkin lymphoma: The Lugano classification. *J Clin Onc* 2014, 32(27):3059-3068

12.3 Appendix: CTCAE Immune System Hypersensitivity Grades

Adverse Event	Grade 1	Grade 2	Grade 3	Grade 4	Grade 5
Allergic reaction	Transient flushing or rash, drug fever <38°C (<100.4°F); intervention not indicated	Intervention or infusion interruption indicated; responds promptly to symptomatic treatment (e.g., antihistamines, NSAIDs, narcotics); prophylactic medications indicated for ≤24 hours	Prolonged (e.g., not rapidly responsive to symptomatic medication and/or brief interruption of infusion); recurrence of symptoms following initial improvement; hospitalization indicated for clinical sequelae (e.g., renal impairment, pulmonary infiltrates)	Life-threatening consequences; urgent intervention indicated	Death
Definition: A disorder characterized by an adverse local or general response from exposure to an allergen.					
Anaphylaxis	-	-	Symptomatic bronchospasm, with or without urticaria; parenteral intervention indicated; allergy-related edema/angioedema ; hypotension	Life-threatening consequences; urgent intervention indicated	Death
Definition: A disorder characterized by an acute inflammatory reaction resulting from the release of histamine and histamine-like substances from mast cells, causing a hypersensitivity immune response. Clinically, it presents with breathing difficulty, dizziness, hypotension, cyanosis, and loss of consciousness and may lead to death.					

Adverse Event	Grade 1	Grade 2	Grade 3	Grade 4	Grade 5
Autoimmune disorder	Asymptomatic; serologic or other evidence of autoimmune reaction, with normal organ function; intervention not indicated	Evidence of autoimmune reaction involving a non-essential organ or function (e.g., hypothyroidism)	Autoimmune reactions involving major organ (e.g., colitis, anemia, myocarditis, kidney)	Life-threatening consequences; urgent intervention indicated	Death
Definition: A disorder resulting from loss of function or tissue destruction of an organ or multiple organs, arising from humoral or cellular immune responses of the individual to his own tissue constituents.					
Cytokine release syndrome	Mild reaction; infusion interruption not indicated; intervention not indicated	Therapy or infusion interruption indicated but responds promptly to symptomatic treatment (e.g., antihistamines, NSAIDs, narcotics, intravenous fluids); prophylactic medications indicated for ≤24 hours	Prolonged (e.g., not rapidly responsive to symptomatic medication and/or brief interruption of infusion); recurrence of symptoms following initial improvement; hospitalization indicated for clinical sequelae (e.g., renal impairment, pulmonary infiltrates)	Life-threatening consequences; pressor or ventilatory support indicated	Death
Definition: A disorder characterized by nausea, headache, tachycardia, hypotension, rash, and shortness of breath; it is caused by the release of cytokines from the cells.					

Adverse Event	Grade 1	Grade 2	Grade 3	Grade 4	Grade 5
Serum sickness	Asymptomatic; clinical or diagnostic observations only; intervention not indicated	Moderate arthralgia; fever, rash, urticaria, antihistamines indicated	Severe arthralgia or arthritis; extensive rash; steroids or intravenous fluids indicated	Life-threatening consequences; pressor or ventilatory support indicated	Death

Definition: A disorder characterized by a delayed-type hypersensitivity reaction to foreign proteins derived from an animal serum. It occurs approximately 6 to 21 days following the administration of the foreign antigen. Symptoms include fever, arthralgias, myalgias, skin eruptions, lymphadenopathy, chest marked discomfort, and dyspnea.
					
Immune system disorders - Other, specify	Asymptomatic or mild symptoms; clinical or diagnostic observations only; intervention not indicated	Moderate; minimal, local or noninvasive intervention indicated; limiting age-appropriate instrumental ADL	Severe or medically significant but not immediately life-threatening; hospitalization or prolongation of existing hospitalization indicated; disabling; limiting self-care ADL	Life-threatening consequences; urgent intervention indicated	Death

Abbreviations: ADL, Activities of daily living; NSAIDs, non-steroidal anti-inflammatory drugs.
Adapted from CTCAE 4.0 – June 14, 2010, Immune system disorders.

## **1 Introduction**

This statistical analysis plan (SAP) describes the statistical methods to be used during the reporting and analyses of data collected under ADC Therapeutics Protocol ADCT-402-101.

This SAP should be read in conjunction with the study protocol and case report form (CRF). This version of the plan has been developed using the protocol Amendment 7 dated 16 October 2017 and CRF version 5 dated 23 Jan 2018.

## 2 Study Objectives

### 2.1 Primary Objectives

- Evaluate the safety and tolerability, and determine, as appropriate, the maximum tolerated dose (MTD) of ADCT-402 in patients with relapsed or refractory B-cell lineage NHL in Part 1.
- Determine the recommended dose(s) of ADCT-402 for Part 2 (expansion).
- Evaluate the safety and tolerability of ADCT-402 in Part 2 (expansion) at the dose level(s) recommended in Part 1.

### 2.2 Secondary Objectives

- Evaluate the clinical activity of ADCT-402 measured by overall response rate (ORR), duration of response (DOR), overall survival (OS), and progression-free survival (PFS).
- Characterize the pharmacokinetic (PK) profile of ADCT-402 (total antibody; drug-to-antibody ratio [DAR]  $\geq 0$ ), pyrrolbenzodiazepine (PBD)-conjugated antibody (DAR  $\geq 1$ ), and free warhead SG3199.
- Evaluate anti-drug antibodies (ADAs) to ADCT-402 in blood before, during, and after treatment with ADCT-402.

[REDACTED]

- [REDACTED]
- [REDACTED]
- [REDACTED]
- [REDACTED]
- [REDACTED]

### 3 Study Design

This is a Phase 1, open-label, dose escalation (Part 1) and expansion (Part 2) study of the safety and tolerability of ADCT-402, used as monotherapy, in patients with relapsed or refractory B-cell NHL. The study will determine the MTD, as well as evaluate the preliminary activity, PK, pharmacodynamics (PD), and other exploratory assessments of ADCT-402.

In Part 1, patients will be assigned to treatment according to a 3+3 dose escalation design and oversight of a Dose Escalation Steering Committee (DESC). The initial dose of ADCT-402 will be 15 µg/kg (Dose Level 1), and the highest allowed dose will be 300 µg/kg. The dose-limiting toxicity (DLT) observation period for dose escalation is 1 cycle. Patients will be entered sequentially to each dose level. No intra-patient dose escalation is allowed. During Part 1, the DESC may expand enrollment at any dose level in which 3 patients have completed the DLT observation period if at least 1 patient in the study has achieved a partial response (PR) or better, or if further evaluation of PK or PD data is deemed necessary to characterize pharmacology in humans. No more than 10 patients in total can be treated at any dose level unless  $\geq 3$  of the 10 patients have achieved a PR or better.

In Part 2, (expansion), all patients will be assigned to the dose level(s) of ADCT-402 identified in Part 1. During dose expansion, patients will be monitored for safety using the same DLT criteria employed during dose-escalation. If during the treatment period, >30% of patients experience safety events that would meet the criteria that define a DLT in the dose-escalation phase of the study, enrollment in the expansion cohort(s) may be paused and the study data reviewed to determine whether additional monitoring or other action (such as alternate dose levels) should be evaluated prior to further enrollment.

#### 3.1 Sample Size Consideration

This is a Phase 1 study with a maximum sample size of up to approximately 200 patients. It is estimated that approximately 90 patients will enroll in Part 1, and approximately 110 patients will enroll in Part 2.

#### 3.2 Randomization

This study is not randomized.

#### 3.3 Modifications to the statistical section of the protocol

The efficacy analysis set was defined in the protocol as all patients with valid baseline data who receive at least 2 doses of study drug or who have documented progression of disease at any time after the first dose of study drug. However, a few patients received 200 µg/kg on an every 6 weeks (Q6W) schedule and their disease assessments were performed before the second dose. These patients should be considered as evaluable for efficacy analysis.

Therefore, the efficacy analysis set is updated in the SAP to include all patients who have received at least one dose of ADCT-402 with a valid baseline and at least one valid post-baseline disease assessment or patients who have documented progression of disease or death at any time after the first dose of study drug.

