4.1.9 End of Treatment Visit

The following procedures will be performed within 30 days after study treatment discontinuation and prior to initiation of new anticancer treatment:

- Physical examination including whole body skin assessment.
- Weight and vital signs.
- ECOG performance status.
- Disease assessments:
 - Patients who already have documented objective disease progression do not need to have assessments repeated.
 - Patients who do not already have documented objective disease progression will have assessments performed at the end of treatment visit if the most recent disease assessment was >9 weeks prior to the end of treatment visit.
- Blood or urine pregnancy test
- Hematology, coagulation panel, and biochemistry parameters.
- Urinalysis and sample collection for additional renal function studies.
- 12-lead ECG.
- Sample collection for central laboratory analysis of PK parameters and ADA.

- 
- Collection of AE information
 - Collection of concomitant medication information.

When EOT coincides with a scheduled visit, the scheduled visit will become EOT.

4.1.10 12-week Follow-up Visit

Each patient will have a blood sample taken for assessment of PK and ADA at 12 (\pm 1) weeks after their last dose of ADCT-402, unless a new anticancer treatment has been initiated.

Blood Sample Collection and Adverse Event Monitoring During Long-Term Follow-up

Patients who test positive for ADAs may be requested to supply additional ADA samples.

For all patients, collection of AEs and SAEs will continue for 12 weeks after the last dose of study drug or initiation of new anticancer treatment (see [Section 6.3.2.2](#)).

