7.4 Analysis Sets

Five analysis sets will be used in this study:

- The Safety analysis set will consist of all patients who receive study drug
- The DLT-evaluable analysis set will consist of all patients in Part 1 who receive study drug and excludes patients who discontinue study drug during Cycle 1 without experiencing a DLT.
- The Efficacy analysis set will consist of all patients with valid baseline data who receive who receive at least 2 doses of study drug or who have documented progression of disease at any time after the first dose of study drug.
- The PK analysis set will consist of all patients who receive study drug and have sufficient concentration data for PK analysis.
- The Pharmacodynamic analysis set will consist of all patients who receive study drug and have sufficient concentration data for analysis.

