#### **4.1.3 Efficacy Analysis Set**

The efficacy analysis set consists of patients who receive at least one dose of ADCT-402 with a valid baseline and at least one valid post-baseline disease assessment or patients who have documented progression of disease or death at any time after the first dose of study drug and before the start of any subsequent anticancer therapy or procedure.

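### SAP 3.3 explains only why patients are added to the efficacy set, but its new definition also drops, without saying so, patients with two or more doses and no post-baseline assessment, all of them non-responders under the protocol

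*SAP*

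**What the plan says.** Protocol 7.4 asks for valid baseline data in the efficacy set and then offers two routes in: "at least 2 doses of study drug or who have documented progression of disease at any time after the first dose of study drug". The two-dose route asks for no post-baseline assessment.

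SAP 3.3 gives one reason for departing from this: "a few patients received 200 µg/kg on an every 6 weeks (Q6W) schedule and their disease assessments were performed before the second dose". It says these patients should count as evaluable, and then gives the new rule: "Therefore, the efficacy analysis set is updated in the SAP to include all patients who have received at least one dose of ADCT-402". Its conditions are a valid baseline together with a valid later assessment or, failing those, recorded progression or death once dosing has begun. SAP 4.1.3 repeats the rule but adds that the progression or death must come before any subsequent anticancer therapy or procedure. SAP 3.3 has no such limit.

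Protocol 7.6.2.1 and SAP 4.9.1 both define ORR as the proportion with CR or PR as best overall response. Neither names the analysis set. SAP 4.9.2, 4.9.4 and 4.9.5 do name the efficacy set, for duration of response, PFS and OS.

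**The concern.** The stated reason calls only for an extra way into the set. The replacement text adds that way in but also takes the two-dose route out. A patient who had two doses and was never reassessed is a non-responder in the protocol set and absent from the SAP set. Whether a patient is ever reassessed can depend on how treatment went, so this exclusion is related to outcome.

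SAP 3.3 is where departures from the protocol are meant to be declared. It prints both definitions, but describes the change only as an inclusion.

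At stake is the ORR by dose level, a secondary endpoint. Part 2 cohorts are planned at about 10 to 20 patients (protocol 7.3), so one or two removals would show in the estimate.

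**Working it through.** The documents give no ORR and no efficacy-set count, so there is no figure of the plan's to reproduce. The check is a comparison of the two definitions, followed by arithmetic on assumed counts.

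**1. Who moves.** Take patients with a valid baseline and no subsequent therapy. Cross four yes/no facts: at least two doses, valid post-baseline assessment, documented progression, death.
- Protocol set: two doses, or progression.
- SAP set: assessment, or progression, or death.

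| Doses | Assessment | Progression | Death | Protocol | SAP |
|---|---|---|---|---|---|
| ≥2 | no | no | no | in | **out** |
| 1 | no | no | yes | out | **in** |
| 1 | yes | no | no | out | **in** |
| 1 | yes | no | yes | out | **in** |

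The other 12 of the 16 patterns do not change: 11 are in both sets and one is in neither. Unassessed two-dose patients who progress or die stay in, and progression may be clinical, since SAP 4.9 accepts clinical progression from the end-of-treatment or disposition page. Under the limit in SAP 4.1.3, unassessed two-dose patients whose progression or death came only after subsequent therapy also leave.

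**2. Can the removed pattern occur?** On the 3-week schedule the first assessment falls within 6 days before Cycle 3 Day 1 (protocol 4.1.2), after the doses on Days 1 and 22. Protocol 4.1.9 requires an end-of-treatment assessment only "if the most recent disease assessment was >9 weeks prior to the end of treatment visit", that is, after more than 63 days. I assume the screening scan counts as the most recent assessment.
- Screening scan on Day -14, end-of-treatment visit on Day 43: 43 + 14 - 1 = 56 days (no Day 0), so none is required.
- Screening scan on Day -28, visit on Day 37: 37 + 28 - 1 = 64 days, so one is required.

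A patient who withdraws consent, is lost to follow-up, or starts new therapy before the first scan can therefore leave with no post-baseline assessment.

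**3. Direction.** Let the protocol set have N patients and R responders, with p = R/N. The SAP removes m patients and adds a, of whom b respond. Nobody among the m can have CR or PR without an assessment, so

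SAP ORR = (R + b) / (N - m + a).

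With a = b = 0 this is R/(N - m), which exceeds R/N whenever m > 0 and R > 0. In general the ORR rises only if b + pm > pa.

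**4. Size, all counts assumed.**

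| N, R | m | a | b | ORR before | ORR after |
|---|---|---|---|---|---|
| 15, 5 | 1 | 0 | 0 | 33.3% | 5/14 = 35.7% |
| 15, 5 | 2 | 0 | 0 | 33.3% | 5/13 = 38.5% |
| 15, 5 | 1 | 2 | 0 | 33.3% | 5/16 = 31.3% |
| 100, 40 | 5 | 0 | 0 | 40.0% | 40/95 = 42.1% |
| 100, 40 | 10 | 0 | 0 | 40.0% | 40/90 = 44.4% |
| 100, 40 | 5 | 10 | 0 | 40.0% | 40/105 = 38.1% |
| 100, 40 | 5 | 10 | 2 | 40.0% | 42/105 = 40.0% |
| 100, 40 | 5 | 10 | 4 | 40.0% | 44/105 = 41.9% |

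Exact 95% intervals: 5/15, 11.8% to 61.6%; 5/13, 13.9% to 68.4%.

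**5. Fit with the rest of the SAP.** SAP 4.9.4 analyses PFS on the efficacy set and censors patients with no post-baseline assessment on Day 1. Under SAP 4.1.3 such patients enter only through progression or death, which are PFS events, so the rule has essentially nobody left to act on. SAP 4.9.1 keeps a patient whose only assessment is SD within 35 days as NE, hence a non-responder, while a two-dose patient with no assessment can vanish from the denominator.

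**The case against.** A reader might infer that the redefinition raises ORR. The documents do not support that. It also admits unassessed one-dose patients who die, all non-responders, and one-dose patients with an assessment, who may or may not respond. The tables show a rise, no change and a fall, all with patients removed.

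A reader might also infer that toxic dose levels will look more active because early stoppers disappear. Protocol 4.1.11 works against this: patients who stop for reasons other than progression are to be scanned about every 12 weeks until progression or new therapy, so a toxicity stopper who stays in follow-up is due an assessment and remains in the set. One-dose toxicity stoppers who are later assessed or die are newly admitted.

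Nor do the documents tie the steering committee's choice of Part 2 doses to this set. It reviews emerging data monthly or more often (protocol 6.3.1.1), and SAP 5 plans no formal interim analysis.

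The ORR denominator is indeed inferred. The inference is reasonable: SAP 4 makes the analysis set the default denominator for percentages, and SAP 4.9.1 uses the efficacy set for its tumour-size analysis.

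These points narrow the concern to a small group and a component effect. They do not explain why the two-dose route was dropped, and offsetting additions do not justify an unstated removal.

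**Conclusion.** The point stands in limited form. SAP 3.3 and 4.1.3 remove patients with at least two doses, no valid post-baseline assessment, and no documented progression or death before subsequent therapy. The stated reason does not require this, and SAP 3.3 does not mention it. All those removed are non-responders in the protocol set, so the removal by itself biases ORR upward: by about 2 to 5 percentage points in the examples above, where 5% to 13% of patients are removed. Those counts are assumptions, and the documents do not show how many patients are affected. The net direction of the whole redefinition is not determined. The conclusion for ORR rests on the efficacy set being its denominator.

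Severity is moderate: ORR is a secondary endpoint in a non-randomized Phase 1 study with no hypothesis testing.

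**What to change.** - In SAP 3.3 and 4.1.3, define the efficacy set as the protocol 7.4 set, plus patients with at least one dose, a valid baseline and a valid post-baseline assessment, plus deaths. This meets the stated reason without removing anyone through loss of the two-dose route.
- In SAP 4.9.1, name this set as the ORR denominator, and count patients with no post-baseline assessment as NE and non-responders.
- Align SAP 3.3 with 4.1.3 on the subsequent-therapy limit, and say whether a valid baseline is also required of patients who enter through progression or death.
- List every membership change in SAP 3.3, including the addition of deaths, which the every-6-week reason does not explain.
- Optionally, add an ORR row on all treated patients.

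The cost is a few sentences. ORR may come out slightly less favourable.
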